Official Title: The Effects of Electrical Muscle Stimulation Exercise on Upper, Lower Extremity and Core Strength in Sedentary Women

NCT Number: Pending

Date: October 7, 2025

Prepared by: [name] [name]

[name]

Institution: 19 Mayıs University

The Effect of Electrical Muscle Stimulation Exercise on Lower, Upper Extremity, and Core Strength in Sedentary Women

Participants

Our study was conducted with 27 sedentary women between the ages of 19-24. The optimal number of subjects to participate in the study was determined using the GPower 3.1.3 program. The results indicated that a total of 16 subjects would be an appropriate sample size for the study (effect size r : 0.87, lower and upper critical p : 0.53, true power: 0.92). Before the study, the subjects were informed in detail and included in the study by obtaining an "Informed Consent Form".

[figure not shown]

Figure 1. Flowchart

Study Design

This study was designed as a 2-arm parallel-group randomized controlled trial comparing

the effects of submaximal EMS exercises. The study was approved by the Ondokuz Mayıs University Clinical Research Ethics Committee (approval number: 021/482) and was conducted as per the ethical principles stated in the Declaration of Helsinki. The inclusion criteria of the participants were determined as being between the ages of 19-24, being female, and volunteering. Exclusion criteria were those who had cardiovascular, neurological, or orthopedic disorders, were pregnant or were planning to become pregnant. Subjects made a total of 10 visits, including the familiarization session for the study. During the first visit, participants were informed about test protocols. Anthropometric measurements were then taken and trial measurements were made. In the pre-, mid (week 4), and post (week 8) test periods, all participants performed 3 visits at 24-hour intervals for a total of 9 visits according to the test protocols they selected from the practice cards specified for each period, and mid and post-tests were arranged so that they did not coincide with training days. Practice cards were as follows: 1- modified push-up (MPU), Handgrip strength (HS), single hop for distance (SH), Biering Sorensen (Bie-sor), 2- Bent arm hanging (BAH), triple hop for distance (TH), crossover triple hop for distance (CH), v-sit flexor (V-sit) and 3- deep squat (DS), medial side triple hop for distance (MSTH), sit-up. After completion of the pre-tests, participants were randomized into one of two exercise groups using computer-validated software (www.random.org) and divided into EMS (n=15) and Control (CON) (n=16) groups. Participants who did not participate in regular exercises and tests in both groups were excluded from the study and the study was completed with 12 participants for the EMS group and 15 participants for the CON group. All measurements and exercises were done at the same time of the day (12:00-16:00). The participants performed warm-up exercises before the tests. Both groups were asked not to make any changes in their usual physical activity behavior. Also, all participants were instructed to maintain their normal dietary intake before and during the study. The endpoint of the study was determined as the participant withdrawing consent to participate in the study, the experts deciding that it was not appropriate for the participant to continue in the study, and non-compliance with the study protocol.

Electro Muscle Stimulation (EMS) Implementation: Participants were instructed that the clothing they would wear during training should be cotton and of a length that would cover their major muscle groups. Then, before the EMS vest was put on, water was sprayed on the main muscle groups where the apparatus that will transmit the current inside it corresponds. After the vest was put on, cable connections were made to the device. Participants were subjected to EMS currents in cardio mode (continuously alternating low-frequency currents

ranging from 1 to 1000 Hz) in a 9 s current/2 s rest pattern for 20 minutes. The muscles stimulated with EMS were: gluteus maximus, quadriceps and hamstrings of the lower extremity, biceps brachii, triceps brachii, pectoralis major and teres major of the upper extremity, and rectus abdominis and latissimus dorsi of the trunk. The content and scope of the exercise to be performed were designed as intermittent, low intensity/low intensity to affect the lower, upper, and core strengths.

Figure 2. EMS Device and Vest

Table 1: Exercise Protocol

Exercise	Rest
Rope skipping – 30 sec×2	10 sec
Overhead stand crunch – 30 sec×2	10 sec
Overhead side bends – 30 sec×2	10 sec
Squats 30 sec×2	10 sec
Sumo squats 30 sec×2	10 sec
Overhead lunge – 30 sec×2	10 sec
Side lunges - 30 sec×2	10 sec
Sit-up -30 sec×2	10 sec
Reverse shuttle -30 sec×2	10 sec
Single leg drop – 30 sec×2	10 sec
Flutter kicks – 30 sec×2	10 sec
V-sit – 30 sec×2	10 sec
Leg hold – 30 sec×2	10 sec
Reverse leg lift – 30 sec×2	10 sec
Heel touch – 30 sec×2	10 sec
Point single leg bridge drop – 20 sec×2	10 sec
Plank – 30 sn×2	10 sec

Procedures

Modified Push Up Test (MPU)

Participants were positioned face down on a mat with only their palms and toes touching the floor. Then, the participants were instructed to start by bending only their elbows and lowering and raising their bodies so that the chest did not touch the floor. The participant repeated as many movements as possible for 30 s and the movement was recorded in units (Chen et al., 2018).

Handgrip Strength Test (HS)

The measurements were made using a hand dynamometer that can measure force between 0-100 kilograms, and the dynamometer was adjusted according to the hand of the athlete to be measured before the measurement. The person to be measured was asked to squeeze with maximum force while standing, with arms hanging down so that the dynamometer did not touch the body. 3 measurements were made, with 1 minute of rest between measurements, and their averages were recorded (Melo et al., 2025).

Bent Arm Hanging Test (BAH)

This test was based on the measurement of the hanging time of the athletes with their arms in full flexion (elbow joint angle less than 75°). During the test, the athlete was verbally warned to remain in the position in question. The test was terminated when the participant's chin dropped below the bar level. The test result was recorded with a CASIO timer as the time the participant could hang under defined conditions (Clemons, 2014).

Single Leg Hop Tests (SLHT)

SLHTs were implemented on a single line by the parameters SH, TH, CH, and MSTH (Reid et al., 2007; Kivlan et al., 2013). For the line to be used in the test, a 0.3 m strip was determined as the starting point, and a 6 m long and 5 cm wide strip extending from the middle was placed vertically. Before starting the test, the test protocol was shown to the subjects verbally and practically. Each participant performed 1 trial forward from the baseline for each test and each limb. They then performed 3 trials for the actual test and the result was recorded in cm. A 30-second rest was given between trials. The best-recorded score was measured between the baseline and the subject's heel. No restrictions were made on arm swings. After the jump, care was taken to ensure that the subject was on the line in the limb that was tested in a controlled manner. The test was repeated if the subject lost balance landed on a limb different from the test limb, or made an additional jump after landing (Kehribar et al., 2022).

Deep Squat Test (DS)

In the deep squat test, individuals place their feet shoulder-width apart with their toes pointing straight ahead. On command, participants stand in the lowest squat position they can reach without lifting their heels off the floor. Although each individual has three attempts, if they complete the test on the first attempt, they do not need to repeat the test (Stanton et al., 2021).

V-Sit Flexor Test

For the V-sit flexor endurance test, testing the endurance of the flexor muscles began with the person being placed in a sitting position and leaning on a jig with the back at an angle of 55

degrees from the floor. Knees and hips were flexed 90 degrees, arms folded across the chest, and feet secured under the strap. To start, the jig was pulled back 10 cm (4 inches) and the person tried to hold it as long as possible without disturbing the posture of the body. Failure in the test was determined to occur when the subject's back was touched or when the subject was asked to stop (Chai et al., 2024).

Sit- Up Test

In the sit-up test, the participant lay on their back on a gymnastics mat and locked their hands behind their neck. The sole was fixed to the mat with the knees at a fixed angle (90°). An aid was used to stabilize the sole. The number of sit-ups the subject would perform for 30 seconds was recorded (Kukic et al.,2022).

Biering Sorensen Test (Bie-sor)

For the Biering-Sorensen-back extensor test, the upper body was extended over the end of a stretcher and then the pelvis, knees, and hips were fixed. The test began after the hands were fixed crosswise on the chest. Failure in the test occurred when the upper trunk broke its horizontal position when it failed to maintain its position after a verbal warning, and when the participant requested to stop (Nuzzo & Mayer, 2013).

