## **The Effect of Electrical Muscle Stimulation Exercise on Lower, Upper Extremity, and Core Strength in Sedentary Women**

### **Statistical Analysis**

SPSS 21.0 package program was used for data analysis. The normality assumption of the data was examined with the Kolmogorov-Smirnov test and it was determined that the variables were normally distributed ( $p>0.05$ ). One-way analysis of variance in repeated measures and Mixed Design Analysis of Variance in Repeated Measures were applied to the data. Sphericity was examined with Mauchly's Sphericity test. The Sphericity Assumed test was used for those with equal variances ( $p>0.05$ ). In cases where variances were not equal ( $p<0.05$ ), the epsilon value ( $\epsilon$ ) was examined and Greenhouse and Geisser tests were used when  $\epsilon<0.75$  and Huynh-Feldt tests were used when  $\epsilon>0.75$ . Bonferroni test was used to determine the intergroup differences. Data were presented as mean and standard deviation and evaluated at a significance level of  $p<0.05$ .

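### The only power statement (r 0.87, critical value 0.53, N 16, power 0.92) does not fit together and is not tied to the planned mixed ANOVA, so power for EMS versus CON is not established

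*Protocol*

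**What the plan says.** The Participants section of the protocol, citing GPower 3.1.3, concludes that "a total of 16 subjects would be an appropriate sample size for the study" and gives the supporting figures as "effect size r : 0.87, lower and upper critical p : 0.53, true power: 0.92". It does not state the test, the outcome, alpha, sidedness, the source of 0.87, a within-subject correlation or a dropout allowance.

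The Study Design section describes two parallel randomised arms measured at three occasions ("In the pre-, mid (week 4), and post (week 8) test periods") on 11 listed tests. Participants were "divided into EMS (n=15) and Control (CON) (n=16) groups", and "the study was completed with 12 participants for the EMS group and 15 participants for the CON group".

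The Statistical Analysis section of the SAP says "One-way analysis of variance in repeated measures and Mixed Design Analysis of Variance in Repeated Measures were applied to the data" and sets the significance level at 0.05. Neither document plans a correlation analysis.

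**The concern.** An effect size called r, reported with a lower and an upper critical value, looks like output from a test of one correlation coefficient. It does not look like a calculation for a two-group, three-occasion ANOVA. The figures also appear not to agree with one another: a correlation as high as 0.87 should clear a cut-off of 0.53 almost every time with 16 subjects.

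This is the only power statement in either document. A reader who takes 0.92 at face value may read a non-significant EMS versus CON result as good evidence of no effect, when a large difference could have been missed. Nothing in the statement says what difference the trial could detect.

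**Working it through.** **Inputs.** From Participants: r = 0.87, critical value 0.53, N = 16, power 0.92. From Study Design: 15 and 16 randomised, 12 and 15 completed, three occasions, 11 tests. From the SAP: level 0.05. Assumed here: two-sided testing, and within-subject correlations from 0.5 to 0.9.

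**Step 1: try to reproduce the stated figures as a correlation test.** This reads the printed 'critical p' as a critical r. Taken literally as a p-value threshold, 0.53 would conflict with the SAP's 0.05.

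- Critical r = t / √(N − 2 + t²). With N = 16, two-sided 0.05, t = 2.145: 2.145 / √(14 + 4.600) = 0.497. One-sided, t = 1.761: 0.426. Neither is 0.53. The two-sided value for N = 14 is 0.532.
- Power with the stated cut-off, by simulation: P(|r| > 0.53 given ρ = 0.87, N = 16) = 0.997. This needs no alpha, because the cut-off is given. The Fisher z approximation agrees: (1.333 − 0.590) × √13 = 2.68, and Φ(2.68) = 0.996.
- To obtain 0.92 at N = 16, ρ would have to be about 0.74 (cut-off kept at 0.53) or the cut-off about 0.755 (ρ kept at 0.87).
- With ρ = 0.87 and two-sided 0.05, 9 subjects already give 0.936, so N = 16 does not follow from the inputs.

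**Step 2: try other meanings of 0.87 at N = 16, level 0.05.**

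| Reading of 0.87 | Power | Fit to 0.53 |
|---|---|---|
| Two-group d, 8 versus 8 | 0.37 | no |
| Paired dz | 0.901 | no (critical t 2.13) |
| f, two groups | 0.899 | no (critical F 4.60) |
| f², one predictor | 0.934 | no |
| f, between-group effect with repeated measures, assumed correlation 0.9 | 0.917 | no (critical F 4.60, no lower limit) |
| Point-biserial, R² | above 0.999 | no |

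Some come near 0.92, but none accounts for 0.53, and the paired reading is a one-group test.

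**Step 3: what the planned comparison can detect.** Let d be the week-8 EMS minus CON difference in SD units.

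*Unadjusted week-8 comparison.* Non-centrality = d × √(n₁n₂/(n₁ + n₂)) = d × √(180/27) = 2.582d, on 25 df. Power is 80% at d = 1.13 and 92% at d = 1.36. At 15 versus 16 these are 1.04 and 1.25.

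*Group-by-time test.* λ = [n₁n₂/(n₁ + n₂)] × Σ(v − v̄)² / (1 − ρ), where ρ is now the within-subject correlation, on 2 and 2(n₁ + n₂ − 2) = 50 df. With differences v = (0, d/2, d), the sum of squares is d²/2. Example at ρ = 0.5, d = 1.24: 6.667 × 0.769 / 0.5 = 10.25, which gives power 0.80.

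| Detectable d | ρ 0.5 | ρ 0.7 | ρ 0.8 | ρ 0.9 |
|---|---|---|---|---|
| 12 v 15, 80% | 1.24 | 0.96 | 0.78 | 0.55 |
| 12 v 15, 92% | 1.47 | 1.14 | 0.93 | 0.66 |
| 15 v 16, 80% | 1.15 | 0.89 | 0.72 | 0.51 |
| 15 v 16, 92% | 1.36 | 1.05 | 0.86 | 0.61 |

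Simulating the 12 versus 15 mixed ANOVA (40,000 trials) at correlations 0.5, 0.7 and 0.9 gave power 0.799, 0.800 and 0.801 at these d, with type I error 0.049. With Bonferroni over 11 tests (0.05/11), the 80% range at 12 versus 15 becomes 1.63 to 0.73.

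**The case against.** **The inconsistency is conditional.** It requires a correlation test, a mislabelled critical value, and 0.87 as the correlation actually entered. That is fair, and the 0.997 should always be quoted with that condition. The missing link to the mixed ANOVA does not depend on it.

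**A label slip may explain most of it.** With a correlation of 0.75, N = 14 and two-sided 0.05, the critical r is 0.532 and power is 0.92, and √0.75 = 0.866 rounds to 0.87. This is the closest reconciliation found. It is conjecture, it relabels the effect size, and it still misses the stated N of 16. Even if true, it describes a correlation test, which says nothing about EMS versus CON.

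**The consequence is limited.** The study is complete, 27 women finished against a stated 16, and no estimate or test uses the 0.92. This stands as a limit on severity. But exceeding a number that was not derived for this comparison does not establish its power.

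**The replacement figures carry their own assumptions.** Also true. Linear divergence is the least favourable pattern for a fixed week-8 difference. If the whole difference appears by week 4, or only after week 4, the sum of squares is 2d²/3 and the 80% range at 12 versus 15 becomes 1.07 to 0.48. The SAP plans no allowance across outcomes, and 11 may undercount because the hop tests are done on each limb. Confidence intervals for the EMS minus CON differences would show precision without an assumed correlation.

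**Conclusion.** The concern holds. Read as a correlation test, the stated r, cut-off and N give power 0.997 rather than 0.92, and no reading tried yields all four figures. Whichever reading is right, neither document connects the statement to the EMS versus CON comparison or to the mixed ANOVA.

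The conclusion is that power is not established, not that it is low. At 12 versus 15 the detectable group-by-time difference at 80% power more than halves, from 1.24 to 0.55 SD, across within-subject correlations of 0.5 to 0.9, and the documents give no value for that correlation. Those figures assume two-sided 0.05 per outcome, equal correlations (sphericity), linear divergence and no multiplicity allowance. The statement should be corrected, but the flaw leaves the trial's estimates untouched.

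**What to change.** Withdraw the figure of 0.92 at N = 16 as support for the between-group comparison, or correct it by giving the actual test, alpha, sidedness, outcome and source of 0.87. In its place report the following as a statement of precision and a limitation, not as a retrospective justification of the sample size:

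> The original power calculation could not be reproduced for the planned analysis. With 12 EMS and 15 CON participants analysed, two-sided 0.05 per outcome and no multiplicity allowance, an unadjusted week-8 comparison detects a standardised difference of 1.13 with 80% power and 1.36 with 92% (1.04 and 1.25 at 15 versus 16). For the group-by-time test, assuming linear divergence, sphericity and a within-subject correlation of 0.5 to 0.9, the detectable week-8 difference is 1.24 to 0.55 at 80% power and 1.47 to 0.66 at 92%.

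Say that linear divergence is the least favourable pattern. If a Bonferroni allowance over the 11 listed tests is adopted, the group-by-time range at 80% power is 1.63 to 0.73. Confidence intervals for the EMS minus CON differences would be a useful companion.

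The cost is one reworded paragraph and a less favourable power statement. Enrolment, tests and estimates do not change.

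### Four of the 31 randomised women are excluded for not taking part after allocation, so the 12 v 15 comparison is a completer analysis open to selection bias of unknown size and direction

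*Protocol*

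**What the plan says.** The Protocol, under Study Design, gives the order of events. Randomisation came after baseline testing: "After completion of the pre-tests, participants were randomized into one of two exercise groups". The women were "divided into EMS (n=15) and Control (CON) (n=16) groups". The exclusion rule follows: "Participants who did not participate in regular exercises and tests in both groups were excluded from the study". The same sentence ends with the result: "the study was completed with 12 participants for the EMS group and 15 participants for the CON group". Under Participants, the Protocol describes the study by the reduced number: "Our study was conducted with 27 sedentary women between the ages of 19-24".

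Study Design also lists the ways a woman's participation could end. These are withdrawal of consent and, in its words, "the experts deciding that it was not appropriate for the participant to continue in the study, and non-compliance with the study protocol".

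The SAP, under Statistical Analysis, states the methods: "One-way analysis of variance in repeated measures and Mixed Design Analysis of Variance in Repeated Measures were applied to the data". The SAP text available defines no analysis set, no rule for missing data and no sensitivity analysis.

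**The concern.** Randomisation makes the 15 and 16 women comparable. It does not do so for the 12 and 15 who remain once women have been removed for what they did after allocation. Attendance can depend on the arm, since only the EMS group had the vest and current, and it can also be related to how much a woman would have gained.

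If the women excluded from EMS would have gained less than those kept, the completer contrast favours EMS. If they would have gained more, it works against EMS. In the control arm the effect runs the other way. Unequal loss is not required: equal losses also bias the contrast if different kinds of women leave each arm.

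The named ANOVA methods, as ordinarily run, need a complete row for each woman (pre, week 4 and week 8), so they do not bring the four back. A reader of the available text cannot tell which way the result might be tilted, or how far it depends on these four women.

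**Working it through.** **Inputs from the Protocol.** Randomised: 15 EMS, 16 control. Completed: 12 EMS, 15 control. Described as the study's size: 27.

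**Counts.**
- Randomised: 15 + 16 = 31. Completed: 12 + 15 = 27, which reproduces the Protocol's figure.
- Excluded: EMS 15 − 12 = 3, 3/15 = 20%. Control 16 − 15 = 1, 1/16 = 6.25%. Overall 4/31 = 12.9%.
- Difference between arms: 20 − 6.25 = 13.75 percentage points. Fisher's exact test on 3/12 v 1/15 (excluded/kept) gives two-sided p = 0.33.

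**How the two contrasts are related.** Let mE and mC be the completers' mean changes. Let dE and dC be how far the excluded women's mean change differs from that of their own arm's completers. Then

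all-randomised difference = [12·mE + 3·(mE + dE)]/15 − [15·mC + (mC + dC)]/16 = (mE − mC) + 0.20·dE − 0.0625·dC.

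This is exact and needs no model. The documents give neither dE nor dC.

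**Illustrative size.** Suppose dE and dC each lie within ±1 SD of change (an assumption, not a bound). The largest shift occurs when their signs differ: 0.20 + 0.0625 = 0.2625 SD. At ±2 SD it is 0.525 SD. The completer standard error, in SD of change, is √(1/12 + 1/15) = 0.387. The ratio is 0.2625/0.387 = 0.68.

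**Simulation with no true effect.** Three of 15 and one of 16 are dropped by a score correlated k with change, with a pre–post correlation of 0.7 (60,000 trials). Both k and the pre–post correlation are assumed. Entries are the bias of the completer change contrast in SD of change, with type I error at a nominal 5%.

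| Pattern of exclusion | k = 0.5 | k = 1 |
|---|---|---|
| Same direction in both arms | 0.105 (6.1%) | 0.212 (12.6%) |
| Related to change in EMS only | 0.161 (7.3%) | 0.329 (16.0%) |
| Opposite directions | 0.223 (9.4%) | 0.445 (27.4%) |

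With k = 0 there is no bias (0.001; 5.1%). Swapping the signs in the opposite-direction case gives the same sizes with negative bias.

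The simulation agrees with the identity. At k = 1, |dE| = 1.64 and |dC| = 1.89, and 0.20 × 1.64 + 0.0625 × 1.89 = 0.446.

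For a group-by-time test over three time points (20,000 trials, compound symmetry 0.7), type I error at k = 0.5 and 1 is 6.1% and 9.3% in the same direction, and 8.1% and 18.8% in opposite directions. It is 5.0% at k = 0.

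**What a mixed model can recover.** If the four women have baselines only, a likelihood analysis of all 31 leaves most of the bias. At pre–post correlation 0.7 with opposite directions, 0.191 of 0.223 (86%) and 0.394 of 0.445 (89%) remain. Over correlations 0.5 to 0.9, between 76% and 96% remains.

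**The case against.** The strongest reply is that this may be ordinary dropout. The Protocol states a rule and then the completing counts; it gives no reason for each woman, and it lists other ways to leave, such as withdrawal of consent. If the four missed both training and testing, they have no week-4 or week-8 values and no measured outcome was thrown away. The part of the SAP not seen may define an analysis set, and the flowchart may give reasons by arm. The loss is four women, and its imbalance is compatible with chance. The larger simulated figures are extremes: k = 1 means that exactly the three lowest changers left EMS, and the opposite-direction case adds that exactly the highest changer left control. Nothing in the documents supports that. A mixed model recovers little without follow-up data, and shifted imputations mostly return the assumptions put in.

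Much of this stands as a limit on what can be claimed. Individual reasons are unknown, no bias has been shown, and the extreme rows carry no evidence about this trial. None of it removes the point. Whether the four are called dropouts or exclusions, the comparison is restricted to women who complied after allocation, and the Protocol's own sentence ties the exclusions to non-participation. A flowchart with reasons would help the reader but would not turn 12 v 15 into an all-randomised analysis. That shifted analyses reflect their assumptions is their purpose: they show how far the four women would have to differ before the conclusion changes.

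**Conclusion.** The concern holds, with high confidence, and should be fixed. As described in the available text, the analysis is a completer comparison of 12 v 15 drawn from 15 v 16 randomised, and it is open to selection bias whose size and direction the documents do not determine. The counts and the identity rest on the Protocol alone. The ±0.26 SD range rests on the assumption that excluded women lie within ±1 SD of their arm's completers. The type I error figures rest on assumed correlations, and run from no inflation when exclusion is unrelated to change to about 27% in the most extreme case. The finding that no all-randomised or sensitivity analysis is described is limited to the SAP text available.

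**What to change.** Add to the SAP, and report accordingly:

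> All 31 randomised women are analysed in their allocated group. No woman with measured outcomes is left out for poor exercise attendance. Continuous outcomes are analysed with a likelihood-based linear mixed model on all available pre, week-4 and week-8 values, and the 12 v 15 completer result is shown beside it. Multiple-imputation analyses shift the four women's change over a range in each arm separately (for example −1 to +1 SD of change, and out to ±2 SD as an extreme), plus a zero-change scenario.

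The imputation sentence is needed because the mixed model recovers little if only baselines exist. Report 31 randomised and 27 completing, with reasons by arm if the flowchart does not already give them. Both documents are written in the past tense, so label these analyses post hoc if the main analysis has already been run. If the analyses disagree, word the conclusion as a completer result. If the unseen part of the SAP already specifies an all-randomised analysis, that element is met.

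**Cost.** No new data collection: SAP wording, a mixed model and a small set of imputation analyses. The estimate may become smaller or less precise. If the four women have baselines only, the mixed-model estimate will change little, and the information will come from the shifted analyses and the reasons by arm.

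### Four of 31 randomised women were excluded for not attending exercises and tests, so the 27 are a completer set and the between-arm comparison is open to bias of unknown direction and size

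*Protocol*

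**What the plan says.** The protocol's Study Design section gives the order of events. Allocation followed baseline: "After completion of the pre-tests, participants were randomized into one of two exercise groups", with 15 assigned to EMS and 16 to control. The exclusion rule comes next: "Participants who did not participate in regular exercises and tests in both groups were excluded from the study". No attendance threshold is attached to it. The outcome of the rule is that "the study was completed with 12 participants for the EMS group and 15 participants for the CON group". The Participants section then describes the study by the reduced number: "Our study was conducted with 27 sedentary women between the ages of 19-24".

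Study Design also lists the grounds on which participation ends. Besides withdrawal of consent, these are "the experts deciding that it was not appropriate for the participant to continue in the study, and non-compliance with the study protocol". Non-compliance is thus an exit from the study, and the text available does not provide for continued testing after such an exit.

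The SAP (Statistical Analysis) says of the models: "One-way analysis of variance in repeated measures and Mixed Design Analysis of Variance in Repeated Measures were applied to the data". The SAP text available names no analysis set and no method for missing results. The flowchart and part of the SAP could not be seen and may cover these matters.

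**The concern.** Randomisation makes the arms comparable as allocated. A rule that removes women for what they did afterwards can undo this, because the reasons for not attending may be related to how a woman was responding and may differ between arms. Using the same rule in both arms does not guarantee that it removes the same kind of woman from each.

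The choice of model adds to the problem. A repeated-measures ANOVA in its usual form drops, for a given test, any woman who lacks one of the three periods, so a partial record contributes nothing even if the woman is kept in the study.

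At stake is what the result means. A comparison of 12 with 15 describes women who kept attending. It need not equal the effect of being assigned to EMS.

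**Working it through.** **Inputs from the protocol.** Randomised: 15 EMS, 16 control. Completed: 12 and 15. Pre-test values should exist for all randomised women, since allocation came after the pre-tests.

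**1. Reproduce the count.** 15 + 16 = 31. Losses are 15 − 12 = 3 and 16 − 15 = 1, so 31 − 4 = 27, which matches the Participants section.

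**2. Compare the losses.**
- EMS 3/15 = 20.0%; control 1/16 = 6.3%; overall 4/31 = 12.9%.
- Difference 0.2000 − 0.0625 = 0.1375, Newcombe 95% CI −0.118 to 0.395.
- Fisher exact test on 3 v 12 and 1 v 15: p = 0.33.

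**3. Size of a possible shift (assumed differences).** Let δ be the completer mean minus the excluded mean in one arm, in SDs of change. With proportion p excluded, the completer mean differs from the mean of the whole arm by p × δ. The between-arm shift is therefore 0.2000 × δ(EMS) − 0.0625 × δ(control). The documents give no value for δ, so a range is shown.

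| δ assumed | Same sign: 0.1375 × δ | Opposite signs: 0.2625 × δ |
|---|---|---|
| 0.5 SD | 0.07 SD | 0.13 SD |
| 1.0 SD | 0.14 SD | 0.26 SD |
| 1.5 SD | 0.21 SD | 0.39 SD |

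The standard error of the difference in the completer set is √(1/12 + 1/15) = 0.387 SD.

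**4. Effect on a 5% two-sided test when there is no true effect.** Noncentral t with 12 + 15 − 2 = 25 degrees of freedom and noncentrality equal to shift/0.387:
- same sign, δ = 0.5 and 1.0: noncentrality 0.18 and 0.36, rejection rate 5.3% and 6.3%;
- opposite signs, δ = 0.5 and 1.0: noncentrality 0.34 and 0.68, rejection rate 6.2% and 10.0%.

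**5. What a mixed model could recover.** This was simulated with no true effect, 15 v 16 women, and equal correlation of 0.5, 0.7 or 0.9 between periods. All four excluded women were assumed to have week-4 results, and one control woman missed week 8 at random. The mixed model was fitted by maximum likelihood with unstructured covariance. Three EMS women missed week 8 by one of these mechanisms:

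| Why the EMS women leave | Completer shift | Mixed-model shift |
|---|---|---|
| Lowest observed week-4 change | about 0.16 to 0.17 SD | about 0.00 SD |
| Lowest unseen week-8 change | about 0.32 to 0.33 SD | 0.23 to 0.26 SD |
| Unrelated to outcome | about 0 | about 0 |

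In the second row roughly a quarter of the bias is removed; for example, 1 − 0.24/0.33 = 27%. In the first row the spread of the two estimates is practically the same (0.38 to 0.39 SD), so there is no gain in precision. If none of the four has a test after allocation, the model has nothing to work with and gains nothing.

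**The case against.** The strongest reply is that this may be ordinary dropout. The rule refers to tests as well as exercises. If the four women did not come to be tested, no usable outcome was discarded and no model can bring one back. That stands: the documents do not show which route any of the four took, or whether any has week-4 or week-8 results. The statement that "all participants performed 3 visits at 24-hour intervals for a total of 9 visits" does not settle it, because it may refer to 31 women or to 27.

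A reader might infer from the schedule that usable data were thrown away. The protocol says "mid and post-tests were arranged so that they did not coincide with training days", so missed training did not by itself prevent testing. With 11 tests on three cards (4, 4 and 3) and one card per visit, a woman who missed a single visit would still have 7 or 8 tests complete. This is hypothetical. One card per visit is a reading of the text, no woman with a single missed visit is described, and scheduling tests on other days does not show that anyone who stopped training came to them.

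It is also fair that the rule, its use in both arms and the arm counts are disclosed, that the δ values are assumptions, and that same-sign differences of up to 1.0 SD leave the error rate near nominal. None of this changes the fact that the set of 27 was formed after allocation by a stated rule based on participation.

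**Conclusion.** The point holds as a risk of bias from the choice of analysis set. It should be acted on because the remedy is cheap, with medium confidence. Three stronger readings are not supported.

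- **That the EMS result is inflated.** The imbalance in losses is compatible with chance, and nothing in the documents indicates how the excluded women would have scored. Direction and size are both unknown.
- **That recoverable results were discarded.** This is possible but not shown.
- **That a mixed model would repair the comparison.** It does so if leaving depends on observed week-4 results, only in small part if it depends on unseen week-8 change, and not at all if no post-allocation tests exist for these women.

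On assumed differences of 0.5 to 1.0 SD the shift is 0.07 to 0.26 SD, less than one standard error (0.39 SD). These are illustrations and not upper limits. The exit reasons, or an analysis-set rule, may be in the flowchart or in the part of the SAP that could not be seen.

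**What to change.** **For the present analysis.** Check the records of the four excluded women. For those who have not withdrawn permission to use their data, include every existing week-4 or week-8 result in the arm to which the woman was randomised, judging completeness test by test. Replace the repeated-measures ANOVA with a linear mixed model for each test (arm, period, arm by period, small-sample degrees of freedom). Show the 27-woman result as secondary, labelled as full attenders. If none of the four has a test after allocation, say so and describe the result as applying to attenders.

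**If the protocol is reused.** Let non-compliance end training only, and still offer the week-4 and week-8 tests unless they would be unsafe.

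**Cost.** Now: a check of four records and their data permissions, and one model per test, with no new visits. On reuse: one sentence, and up to 3 visits × 2 periods = 6 test visits per affected woman. The downside is that the estimate will include women who trained little and may be smaller.
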